4.1.1 Rationale for choice of interventions

Two interventions will be evaluated. Intervention 1 is pre- and post-operative hospital-supervised exercise training. Intervention 2 is pre- and post-operative home-supported exercise training.

The hospital based exercise will comprise, in the pre-operative period, a 45 minute exercise counselling session followed by 12 aerobic interval exercise sessions 3-4 weeks prior to surgery and two home-based resistance exercise sessions per week. Post-hospital discharge there will be monthly booster supervised sessions up to 12 months post-randomisation and patients will be encouraged to comply with the NHS England Chief Medical Officer current physical activity recommendations throughout this time period.

The home based exercise intervention will comprise, in the pre-operative period, a 45 minute exercise counselling session followed by a home-exercise programme where participants will be encouraged to comply with current physical activity recommendations: a minimum of 150 minutes of moderate aerobic exercise per week, in the 3-4 weeks prior to surgery and two resistance exercise sessions per week. Post-hospital discharge participants should continue their exercise regime and will receive monthly telephone support from a member of the Trial Intervention Team up to 12 months post-randomisation.

Systematic review evidence suggests that the optimal aerobic exercise intensity for inducing cardiorespiratory adaptations in sedentary older adults is 66-73% heart rate reserve (HRR; ~66-73% VO2 max; Borg RPE Scale: 13-15) (Huang et al., 2015). As aerobic interval exercise programmes (incorporating interpolated rest intervals) enable a greater volume of higher intensity exercise to be achieved, this system of exercise training can help elderly individuals who are less accustomed to physical exertion to maintain

exercise intensity in the optimal range for cardiorespiratory adaptations. This is supported by our recent feasibility work, which showed that cancer patients tolerate and respond well to pre-operative aerobic interval training programmes at 60-80% HRR (Borg RPE Scale: 13-15) using a cycle ergometer, with improvements in anaerobic threshold and peak VO2 being evident after a median of 6 exercise sessions over 3-4 weeks.

Cardiopulmonary exercise testing (CPET) will be used as an objective method of evaluating oxygen transport and utilization during a dynamic exercise challenge and it reflects the ability of the cardiopulmonary system to deliver oxygen to the tissues under conditions of stress. Evidence from systematic reviews and more recent studies suggests that CPET variables can reliably predict patients at increased risk of post-operative complications and morbidity following major surgery for abdominal cancers, aortic aneurysm repair, thoracic surgery and colonic surgery (Benzo et al., 2007, Smith et al., 2009, Thompson et al., 2011, West et al., 2013).

Small-scale feasibility studies have reported improvements in functional outcomes following supported home-based aerobic exercise in conjunction with progressive resistance exercise in cancer patients before surgery (Timmerman et al., 2011, Carli et al., 2010, Li et al., 2013). There is also evidence that such programmes can be successfully continued soon after major cancer surgery (Li et al., 2013, Gillis et al., 2012) and patients who engaged in structured exercise programmes before and after their operation had significantly better functional capacity up to 8 weeks post-surgery (Li et al., 2013). A recent prospective study using similar methodology, pre-operative aerobic interval training, delivered as a hospital based intervention for colorectal cancer patients following post-chemoradiotherapy demonstrated changes in physical fitness following a short programme (6 weeks) of exercise and reported over 90% compliance (West et al., 2015).

The potential role of post-operative exercise programmes for helping to optimise long-term recovery after major abdominal cancer surgery has also been recognized. Preliminary evidence suggests that pre-operative exercise promotes better adherence to post-operative exercise (Gillis et al., 2012) and epidemiological data shows that a physically active lifestyle after curative colorectal cancer treatment enhances survival (Meyerhardt et al., 2006).

This trial aims to produce definitive evidence of the clinical efficacy of pre- and post-operative exercise training on short and longer-term recovery outcomes in cancer patients undergoing major lower-gastrointestinal surgery. In addition, the trial will provide valuable cost-effectiveness data to underpin new clinical guidance on how to implement exercise programmes for cancer patients awaiting and recovering from major abdominal surgery.

4.1.2 Explanation for choice of comparator

The comparator for both Intervention 1 and Intervention 2 is standard care/treatment as usual. Patients are not given advice on exercise pre- or post-surgery other than what is routinely offered within the Trust.

IRAS No: 200804

4.2 Objectives

There are three trial arms:

- Arm A Hospital based supervised exercise
- Arm B Home based supported exercise
- Arm C Standard care, treatment as usual

There are two primary research hypotheses:

- hospital-supervised exercise training in the pre- and post-operative period, in addition to standard care, leads to fewer post-operative complications by day 30 and improved HR-QoL, measured via SF-36, at 12 months post-randomisation versus standard care alone.
- home-supported exercise training in the pre- and post-operative period, in addition to standard care, leads to fewer post-operative complications by day 30 and improved HR-QoL, measured via SF-36, at 12 months post-randomisation versus standard care alone.

The exploratory research hypothesis is that pre- and post-operative hospital-supervised exercise training will lead to greater improvements in cardiopulmonary fitness and fewer post-operative complications, leading to greater improvements in HR-QoL, measured via SF-36, after 12 months, than pre- and post-operative homesupported exercise.

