5.5 Outcomes

5.5.1 Primary Outcomes

Two primary outcomes will be used:

Short Term Outcome; 30-day morbidity

30-day morbidity will be assessed using the Clavien-Dindo classification of post-operative complications (Clavien et al. 2009), for standard care versus hospital based and standard care versus home based interventions. Data will be collected 30 days post-operation by the clinical team, who are blinded to treatment intervention, using a structured set of questions during the routine post-operative review.

Long Term Outcome; health related quality of life

Health-related quality of life will be assessed by the Medical Outcomes Study Health Questionnaire (SF-36) (Ware et al., 1992) (total score) at 12 months post-randomisation, for standard care versus hospital based and standard care versus home based interventions.

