5.7 Sample Size

An overall sample of 1146 patients (randomised 1:1:1) provides 90% power.

Post-operative complications are evident in 55% of patients by day 30 in patients receiving standard care. To detect a 25% reduction (relative risk 0.75) between standard care and each of the exercise groups (90% power, alpha 2.5%) 343 patients are required in each arm, giving 1029, 10% attrition rate - Total 1146. Average SF 36 score at 1 year is 52 SD 10.To detect a 3 unit difference between standard

care and each of the exercise groups (90% Power, alpha 2.5%) requires 276 in each arm, 3 arms 828, 20% attrition rate. Total 1035.

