5.10.4.6 Efficacy Analyses

The group comparisons which will be made are: a) TAU vs Hospital Based Supervised Exercise; b) TAU vs Home Based Supported Exercise; and c) Hospital Based Supervised Exercise vs Home Based Supported Exercise. The comparison a) and b) are the primary comparison and c) is an exploratory comparison as it is not possible to adequately power this comparison. No adjustment is made for multiple testing due to the number of groups as we are treating the comparisons a) and b) as separate research questions so we do not need to control the type 1 error/false positive rate.

For all 3 comparisons with the primary outcomes we will have a significance level of 2.5% to account for having two primary outcomes, this is based on the Bonferroni adjustment of dividing the significance level by the number of comparisons made for each research question. For all secondary outcomes the significance level will be 5%.

Within each group comparison for all continuous outcomes, a general linear model will be used to compare the average values between groups adjusted for the site as the randomisation is stratified by site. Depending on the number of individuals recruited at each site, site will be included as either a fixed or random effect. Assumptions will be checked graphically and if appropriate transformations will be used, if none are appropriate then a Bootstrap will be used. For binary outcomes a logistic regression model will be used adjusting for site.

In addition to the above analysis if any factor is imbalanced at baseline or is considered prognostic by discussion with the PI/TMG/DMC they will be included in an adjusted model. However, the primary analysis is the unadjusted analysis and the adjusted analysis exploratory.

If appropriate, that is to say that there is a large amount of non-adherers to the intervention, then a Complier Average Causal Effect (CACE) analysis will also be undertaken.

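### The fixed 2.5%/2.5% split between the two primary outcomes is valid but gives power away that Holm's procedure would keep, and the joint wording of the hypotheses in 4.2 does not match the separate tests in 5.10.4.6

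*Protocol*

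**What the plan says.** Section 4.2 opens its hypotheses with "There are two primary research hypotheses", one per exercise arm. Each says that the programme "leads to fewer post-operative complications by day 30 and improved HR-QoL, measured via SF-36, at 12 months post-randomisation versus standard care alone". That makes two hypotheses rather than four, with the outcomes joined by one conjunction.

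The other sections keep the outcomes apart. Section 5.5.1 says "Two primary outcomes will be used" and defines a short-term and a long-term one. Section 5.10.4.2 lists them as separate items. Section 5.7 begins "An overall sample of 1146 patients (randomised 1:1:1) provides 90% power" and then gives one calculation for complications and one for SF-36, each labelled with 90% power and alpha 2.5%.

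Section 5.10.4.6 sets the test rule: "For all 3 comparisons with the primary outcomes we will have a significance level of 2.5% to account for having two primary outcomes", and "this is based on the Bonferroni adjustment of dividing the significance level by the number of comparisons made for each research question". It makes no adjustment across the two arm comparisons, because "we are treating the comparisons a) and b) as separate research questions so we do not need to control the type 1 error/false positive rate". The rule is therefore a fixed Bonferroni split of 5% into 2.5% and 2.5% within each arm comparison.

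**The concern.** Dividing alpha between two outcomes is needed when a positive result on either can support a claim. The wording of section 4.2 suggests that both are needed. A reader who takes section 4.2 literally and one who follows section 5.10.4.6 will describe the same result differently, so the hypotheses should be worded to match the test rule.

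The larger practical point is efficiency. Once one outcome has passed 2.5%, a fixed Bonferroni split still holds the other to 2.5%, although the 5% error per comparison would allow it to be tested at 5%. Suppose complications give p = 0.02 and SF-36 gives p = 0.04. The written rule claims complications only, while Holm claims both at the same error rate. With p = 0.01 and p = 0.20 the two rules agree: a claim on complications and none on SF-36.

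**Working it through.** **Inputs (section 5.7).** Complications: 55% under standard care, relative risk 0.75 (so 41.25%), 343 per arm, 10% attrition. SF-36: difference 3, SD 10, 276 per arm, 20% attrition. Power 90% and alpha 2.5% for each; total 1146. The protocol does not state sidedness. Two-sided is assumed, because one-sided 2.5% gives only 276 to 290 per arm for complications and 234 for SF-36.

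**Step 1: reproduce the plan.** The normal quantiles are 2.2414 (two-sided 2.5%) and 1.2816 (90% power).
- SF-36: n = 2 × [10 × (2.2414 + 1.2816) / 3]² = 275.8, so 276. Then 276 / 0.8 = 345, and × 3 = 1035. Both agree with the plan.
- Complications: 326 per arm uncorrected and 340 with continuity correction, against 343 stated (within 3%). Then 343 / 0.9 = 381.1, so 382, and × 3 = 1146, as stated.

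**Step 2: per-outcome power at 1146.** Each arm has 382 randomised: 382 × 0.9 = 343.8 evaluable for complications and 382 × 0.8 = 305.6 for SF-36.
- Complications: pooled standard error √(2 × 0.48125 × 0.51875 / 343.8) = 0.03811; unpooled √[(0.55 × 0.45 + 0.4125 × 0.5875) / 343.8] = 0.03775. Power = Φ[(0.1375 − 2.2414 × 0.03811) / 0.03775] = Φ(1.380) = 91.6%.
- SF-36: standard error 10 × √(2 / 305.6) = 0.809. Power = Φ(3 / 0.809 − 2.2414) = Φ(1.467) = 92.9%.
- At 5% instead of 2.5%, the same formulas give 95.2% and 96.0%.

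The 90% per outcome is met.

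**Step 3: Bonferroni against Holm when the test statistics are independent.**
- Both outcomes, Bonferroni: 0.9162 × 0.9288 = 0.851.
- Both outcomes, Holm: both below 5%, less the case where both lie between 2.5% and 5%. 0.9519 × 0.9598 − (0.9519 − 0.9162) × (0.9598 − 0.9288) = 0.9136 − 0.0011 = 0.9125.
- Complications, Holm: 0.9162 + (0.9519 − 0.9162) × 0.9288 = 0.949.
- SF-36, Holm: 0.9288 + (0.9598 − 0.9288) × 0.9162 = 0.957.

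**Step 4: allow for correlation.** The protocol gives no correlation between the two test statistics, so 0 to 0.75 is an assumed range (bivariate normal). The last column is the chance of any false rejection in one arm comparison when neither outcome is affected. It is the same for both rules, because the first rejection needs p < 2.5% under either.

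| Correlation | Both, Bonferroni | Both, Holm | Complications, Holm | SF-36, Holm | Error, no effect on either |
|---|---|---|---|---|---|
| 0 | 85.1% | 91.2% | 94.9% | 95.7% | 5.0% |
| 0.5 | 86.7% | 91.9% | 94.4% | 95.2% | 4.6% |
| 0.75 | 88.2% | 92.6% | 94.1% | 94.8% | 4.2% |

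**Step 5: when only one outcome is affected.** Holm then gains almost nothing. For complications with no SF-36 effect and independence, power is 0.9162 + (0.9519 − 0.9162) × 0.025 = 0.917, against 0.916.

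**The case against.** The strongest reply is that nothing here is an error. Sections 5.5.1, 5.7, 5.10.4.2 and 5.10.4.6 describe one consistent design, no passage says that both outcomes must succeed, and the sentence in section 4.2 is ordinary prose listing expected benefits. This stands.

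It also disposes of two stronger readings. A reader might infer that a split result has no defined verdict. The protocol does not support that: section 5.10.4.6 gives each outcome its own 2.5% test, so significance on one and not on the other has a clear per-outcome answer. A reader might also infer from the opening line of section 5.7 that the 90% is overstated, since power for both outcomes at 2.5% each is below 90% over the range in the table. But section 5.7 attaches 90% to each outcome and never claims joint power.

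On Holm, the reply is that fixed Bonferroni is simple and valid, and that complications are known at 30 days but SF-36 only at 12 months. The first part is true, so Holm is an efficiency gain and not a repair. The timing point carries little weight, because section 5.11.2 plans no efficacy interim analysis. It leaves one small consequence: a complications p-value between 2.5% and 5% can be judged only once SF-36 is analysed.

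**Conclusion.** The point holds as a modest improvement with a wording mismatch. Type I error is not inflated, the sample size of 1146 stands, and the per-outcome power claim is met (91.6% and 92.9%). What remains is that the joint wording in section 4.2 does not match the separate tests elsewhere, and that the fixed split is needlessly conservative. Within one arm comparison, Holm adds about 2 to 3 percentage points of power per outcome and about 4 to 6 points for both outcomes, at the same 5% error.

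These gains rest on the section 5.7 effects being real for both outcomes, on two-sided testing, on the stated attrition, and on the assumed correlation of 0 to 0.75. They refer to the planned 382 per arm. The two-arm period in section 5.12 changes the numbers per arm and is not modelled here.

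**What to change.** 1. **Section 5.10.4.6.** Replace the fixed Bonferroni split by Holm within each arm comparison: test the smaller of the two primary p-values against 2.5% and, if it passes, the other against 5%. Add that a significant result supports a claim on that outcome only.
2. **Section 4.2.** For each programme, write two separately claimable statements, one on complications by day 30 and one on SF-36 at 12 months.
3. **Section 5.7, opening line.** Say that 1146 patients give 90% power for each primary outcome.

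**Cost.** No extra patients, visits or data. Confidence intervals that match Holm exactly are less simple than those for a fixed split, and a complications p-value between 2.5% and 5% must wait for the SF-36 result. Section 6.3 lists changes to analyses among substantial amendments, so item 1 needs ethics approval. Items 2 and 3 are clarifications that can travel with it.

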4.2.1 Primary objectives

- To establish the effectiveness and cost-effectiveness of hospital-supervised and home supported pre-operative and post-hospital discharge exercise programmes in relation to short-term recovery outcomes and HR-QoL, measured via SF-36, at 12 months in cancer patients undergoing major colorectal cancer surgery.
- 2. To generate robust research and cost-effectiveness data that will underpin clinical guidance on how exercise programmes should be implemented in the routine management of patients undergoing major colorectal cancer surgery.

4.3 Trial Design

This is a multi-centre, 3-arm, randomised controlled trial, to investigate the clinical and cost effectiveness of exercise interventions for cancer patients awaiting curative, elected colorectal cancer surgery.

4.3.1 Internal Pilot Phase

An internal pilot phase has been designed to allow an assessment of stop/go criteria for progression to a full trial. At the end of this phase a decision will be made by the funder, in consultation with the TSC and IDMC, on whether or not to proceed with the trial. Recruitment will continue while data on patients in the internal pilot are analysed and reviewed by the TSC and IDMC and a funder decision is obtained. As an internal pilot, all data collected on study participants will be included in the further analyses.

The objectives of the internal pilot phase (to run for 1 year following 6 month site set-up) are to confirm feasibility of:

- 1. Site set-up
- 2. Site recruitment
- 3. Acceptability of the exercise intervention
- 4. Adherence to the respective exercise interventions

The stop/go criteria are:

- 1. Site set-up 75% of sites open at recruitment month 12.
- 2. At least 30% of eligible patients recruited to the study. This will be closely monitored throughout the recruitment phase of the trial.

- 3. Recruitment demonstrate that 50% of sites can reach recruitment rates sufficient to sustain the phase II study, i.e. 4-5 patients per month during recruitment months 10-12.
- 4. Meaningful adherence to the study arms (minimum of 6 pre-operative supervised sessions in at least 70% of patients and 50% of post-operative booster sessions in at least 70% of patients.

5 Methods

5.1 Site Selection

The trial sponsor has overall responsibility for site and investigator selection and has delegated this to the Co-Chief Investigators and NCTU.

5.1.1 Study Setting

Participants will be identified from colorectal units, at point of diagnosis. Initially the following sites will be opened, but with the intention to open further sites as the study progresses. The collaborating sites identified at study start-up are: Norfolk and Norwich University Hospitals NHS Foundation Trust, Northumbria Healthcare NHS Foundation Trust, Sheffield Teaching Hospitals NHS Foundation Trust, Cambridge University Hospitals NHS Foundation Trust, Derby Teaching Hospitals NHS Foundation Trust, Imperial College Healthcare NHS Trust, Royal Devon and Exeter NHS Foundation Trust, Western General Hospital Edinburgh, Central Manchester University Hospitals NHS Foundation Trust, Peterborough and Stamford Hospitals NHS Foundation Trust and Colchester Hospital University NHS Foundation Trust.

The exercise interventions will take place in hospitals and in the community depending on the treatment arm to which the participant is allocated.

5.1.2 Site/Investigator Eligibility Criteria

Once a site has been assessed as being suitable to participate in the trial, the trial team will provide them with a copy of this protocol, and at least one person to lead the Trial Intervention Team will be identified from each site to undergo intensive training on how to deliver the intervention.

To participate in the PREPARE-ABC trial, investigators and trial sites must fulfil a set of criteria that have been agreed by the PREPARE-ABC Trial Management Group (TMG) and that are defined below.

Eligibility criteria:

- A named clinician (surgeon, anaesthetist or physiotherapist) is committed to take Principal Investigator responsibility.
- Suitably trained staff are available to recruit participants, enter data and provide support
- A named Trial Intervention Team Lead available to fulfil the requirements of the trial
- A named lead to coordinate CPET testing (if available)
- The site is able to identify a suitable number of patients, this will vary depending on the location and size of the hospital, the study has been designed to include and represent a good cross section of sites. Recruitment targets will be discussed with each centre.
- The site is not currently delivering either the hospital supervised or home based intervention as standard care

Trial sites meeting eligibility criteria and that are accepted by the TMG as being suitable to recruit to the trial, will be issued with the PREPARE-ABC Trial Master File (TMF) documentation to use when applying for Site-Specific Approval (SSA) or local institutional approval as applicable.

5.1.2.1 Principal Investigator's (PI) Qualifications and Agreements

The Investigator(s) must be willing to sign an Investigator Agreement to comply with the trial protocol (confirming their specific roles and responsibilities relating to the trial, and that their site is willing and able to comply with the requirements of the trial). This includes confirmation of appropriate qualifications, agreement to comply with the principles of GCP, to permit monitoring and audit as necessary at the site, and to maintain documented evidence of all staff at the site who have been delegated significant trial related duties.

5.1.2.2 Resourcing at site

The Investigator(s) should be able to demonstrate a potential for recruiting the required number of suitable participants within the agreed recruitment period (i.e. the Investigator(s) regularly treat(s) the target population). They should also have an adequate number of qualified staff and facilities available for the foreseen duration of the trial to enable them to conduct the trial properly and safely.

Sites will be expected to complete a delegation of responsibilities log and provide staff contact details.

The site should have sufficient data management resources to allow prompt data return to NCTU.

